## INTRODUCTION

Although the severity of symptoms varies from one subject to another (Joyce & Roiser, 2007), 75% of people with schizophrenia present cognitive dysfunctions (Heinrichs et.al, 2013), even before the first expression of symptoms (Brewer et al., 2005; Sheffield et al., 2018), being a basic characteristic (Green et al., 2019) in all phases of the disease (Rajji et. Al, 2014). These deficits in brain areas involved in attention, memory, social cognition, executive functions, and metacognition have a great impact on the daily functionality of affected people, often preventing them from enjoying a satisfying and full life.

Due to the limitation observed with pharmacological treatments to improve cognitive deficits in people with Severe Mental Disorder (SMD) (Ciceri , Ocampo & Franco, 2008) , it is essential to offer alternative treatments to work in this area. Although most of the research in relation to cognitive training is frequently linked to schizophrenia, in recent years it has been developed for other disorders, showing its great benefit in improving cognitive processes (Keshavan et al., 2014). Taking advantage of brain neuroplasticity to influence the cognitive capacity of affected people, many interventions have been developed. In the present study, we will focus on dance

therapy as a vehicle for the modulation of the neural system, achieving improvement in cognitive areas such as executive functions.

The concept of Dance Movement Therapy (DMT) is a psychotherapeutic technique that allows the person to engage in a creative and relational process (Association for Dance Movement Psychotherapy UK (ADMP UK), 2023) providing emotional, social, cognitive and physical integration (American Dance Therapy Association (ADTA), 2020) and personal growth (Panhofer & Rodríguez, 2005) seeking an improvement in their health and well-being. DMT is considered an intervention with the potential to prevent and treat physical and cognitive decline (Vergheze, 2003). In terms of cognition, a study with a quasi-experimental design of matched controls that proposed a 60-minute group aerobic dance class, 3 times a week for 3 months, showed that DMT can be a technique that allows significant improvements in processing speed, memory and executive function, in people with schizophrenia (Chen et al., 2016). However, research related to DMT lacks data on the neurophysiological mechanisms that are possibly affected by the application of these types of interventions. The use of the electroencephalogram (EEG) allows us to obtain additional measurements on possible changes in brain connectivity that can contribute to a detailed quantification of the therapeutic effects of DMT (Ventouras et al., 2015).

These therapeutic approaches differ from cognitive, behavioral and other usual therapies based mainly on interaction, as well as communication and verbal expression. As has been previously reported, DMT suggests cognitive benefits (Tan et al., 2016), symptomatological (Lee et al., 2015), as well as functional remission (Gökcen et al., 2020) and quality of life (Kaltsatou, 2015) for people with SMD. However, there are major limitations in the previous literature regarding the study of this program. Therefore, further analysis is needed to determine the benefit of DMT on cognition (memory and executive functions) in people with SMD. For these reasons, it becomes critical to conduct research with a consistent theoretical framework and experimental design; that demonstrates the effectiveness of DMT. For all of the above reasons, this study proposes to analyze the effects of dance therapy on the cognition of people with SMD, using psychometric and neurophysiological techniques. These findings would allow us to modulate the interventions currently

offered, towards more effective protocols, improving the quality of life of people with SMD and thus report significant impacts on their interpersonal relationships and functionality.

## **HYPOTHESIS AND OBJECTIVES**

### **1. Hypothesis**

According to the evidence from the literature, it is proposed that participation in a therapeutic dance therapy program will have a significant positive effect on the scores of neurocognitive tests and on the electroencephalographic activity patterns of patients diagnosed with severe mental disorder (SMD). Specifically, it is expected that after the intervention, participants will show significant improvements in memory and executive functions compared to the control group without intervention.

From a more theoretical perspective, our null and alternative hypotheses are:

- Null Hypothesis (H0): there is no significant difference between the neurocognitive test scores and the electroencephalographic activity patterns of people with SMD who participate in a dance therapy therapeutic program and those who do not.
- Alternative Hypothesis (H1): Participation in a therapeutic dance therapy program will have a significant positive effect on neurocognitive test scores and electroencephalographic activity patterns of people diagnosed with SMD.

Specifically, it is expected that after the intervention:

- H1a: People participating in the dance therapy program show significant improvements in memory test scores compared to the control group.
- H1b: People participating in the dance therapy program show significant improvements in executive functions compared to the control group.

Our hypothesis is based on a solid theoretical foundation, which suggests that dance therapy could promote neuroplasticity and improve cognition through body movement. To this end, we will conduct this carefully controlled study, collecting pre and post intervention data in both groups and using appropriate statistical analyses.

To test this hypothesis, a controlled study will be carried out with an experimental group participating in the dance therapy program and a control group that will not. Neuropsychological test scores and electroencephalography data will be compared before and after the intervention to assess any significant changes in cognitive function and brain activity.

A valuable contribution of this research is the possibility of improving the quality of life of people with SMD through novel interventions such as dance therapy. Furthermore, it is worth highlighting the relevance of this study for the scientific and clinical community, where health personnel in hospitals, detention centers and shelters for patients with SMD are completely overwhelmed in a society where the number of people with mental disorders continues to increase.

In this study, we will also ensure that we address ethical issues such as informed consent of participants and consideration of their well-being throughout the study. Our priority is that research in the field of mental health and therapy is conducted in an ethical, rigorous and respectful manner.

## **2. Main objective**

- To evaluate the impact of a therapeutic dance therapy program on cognitive functions, specifically on memory and executive functions, in patients diagnosed with severe mental disorder by measuring scores on neurocognitive tests such as the BACS and MOCA (subsequently defined in the section on data collection) and by analysing electroencephalographic activity.

## **3. Secondary objectives**

- 1) To compare the scores obtained from the neurocognitive test battery between the experimental group and the control group.
- 2) To compare the changes in brain activity patterns recorded by electroencephalography between the experimental group and the control group.
- 3) To analyze the changes generated in both groups in order to be able to identify the

possible correlations between the improvement in cognitive functions and the alterations in brain activity.

- 4) To evaluate the effects of a 20-session dance therapy program on the symptomatology of people with SMD using the PANSS (later presented in the section on data collection).

## **STUDY METHODOLOGY**

### **1. Design**

A single-centre prospective randomised controlled trial will be conducted with a minimum of 47 patients with severe mental disorder (SMD) who will be randomly assigned into two groups, 1 intervention group receiving dance therapy (n=26) and 1 control group who will not receive any intervention or added treatment apart from continuing with their usual treatment (pharmacological), but will not receive intervention with dance therapy (n=21).

In summary, the groups are:

- Experimental group (n=26): people with SMD receiving dance therapy.
- Control group (n=21): people with SMD who do not receive the dance therapy intervention but do receive their usual pharmacological treatment.

Tests will be administered before the start of the study and at the end of the study, as well as 3 months after the end of the study in order to compare the results between groups.

### **2. Study population.**

#### **a. Population characteristics**

Patients who will participate in the dance therapy program will be referred to the Canarian Association of Creative Therapies (ASCATEC) through the Mental Health Units of the Canary Islands according to a referral program of the Government of the Canary Islands. They will be selected according to the criteria listed below without distinction of age, sex, gender or type of diagnosis, as long as they meet the main diagnosis of SMD.

The assignment will be made randomly, as they will be referred by the Government of the Canary Islands (see point 6.4.1.2. Coordination between devices in the mental health network of the Mental Health Plan in the Canary Islands 2019-2023, p.179-180).

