**e. Sample size calculation.**

The present study aims to determine the number of participants needed to determine the effect of a dance therapy program administered to patients with severe mental disorders. Preliminary studies cited in the literature have determined that dance therapy has the potential to influence aspects such as emotional state, memory or executive functions, being observable through neuropsychological and EEG tests. The working hypothesis is that dance therapy will produce a statistical effect, involving cognitive improvement, observable in subsequent assessments of neuropsychological test scores and electroencephalographic activity patterns in those diagnosed with severe mental disorder. Therefore, in this study we tried to determine two independent sample means.

The calculation of statistical power was performed by means of two independent ("unilateral") means, based on the variance of a control group and the reference group with a minimum of 13 study subjects, in accordance with systematic reviews of previous scientific studies such as Jiménez et al. (2019). The probability of the degree of statistical significance was based on values of  $p<0.05$  with the statistical tests applied, with a 95% confidence interval.

The sample was calculated using GRANMO software (Marrugat et al., 1998). In this line, in order to estimate the probability that the observed phenomenon is true and not due to chance with the calculated sample size, the alpha risk was determined. Specifically, an  $\alpha=0.05$  was chosen, which assumes a 95% confidence level. To control for the potential of the analysis, a power of 80% was selected, with a beta of 0.2. To define the ratio between two groups (control and experimental), the ratio between group 1 and group 2 was indicated, the ratio being a value of 1, as these are two groups with equal sample sizes. In addition, as we are calculating on the basis of means, the standard deviation has been included. Since we do not have a pilot project with previous data before and after the dance therapy program proposed in the current project, the following process was used to find the standard deviation:

1. Review of previous literature on mental health and dance therapy; 2. Screening of dance therapy manuscripts with patients presenting with a pathology encompassed

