Therefore, considering the respective loss to follow-up rates in both the experimental group and the control group, the final (n) for each group would be as follows: experimental group with an  $N=28$ , after expected loss to follow-up of 10% out of 28

equals 2.8 participants, would be left with a final (n) of 26 participants; control group with an N=28, after expected loss to follow-up of 25% out of 28 equals 7, would be left with a final (n) of 21 participants.

In conclusion, for this project we need 47 participants (21 participants for the control group and 26 participants for the experimental group receiving intervention with dance therapy). It is also worth mentioning that each participant will sign a pre-test consent to participate in data acquisition and, if applicable, intervention in the dance therapy program as part of the research project. These consents will inform them of the aims of the study, risks if applicable, and answer any questions or queries they may have.

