## **PROCEDURE or DESCRIPTION OF THE STUDY**

### **1. Workplan**

All the tests (BASC, MoCA, PANSS and EEG) will be carried out with the 47 patients with SMD to find out their baseline status. The people with SMD will be randomly assigned to an experimental group (dance therapy program) or a control group (without intervention in dance therapy but with regular pharmacological treatment). The study will last approximately 1 year between the administration of tests, the program and the analysis of results. The dance therapy program will last 20 sessions over 10 weeks. The sessions will take place at the headquarters of the Asociación Canaria de Terapias Creativas (ASCATEC) in the Siglo XXI space in Santa Cruz de Tenerife.

The 26 people with SMD in the experimental group will participate in a 10-week intervention program with 2 sessions per week in which they will work for 1 hour on memory, attention and executive functions through dance and movement, ending with 10 minutes of Mindfulness.

The 21 people in the control group will not receive any type of dance therapy intervention, but will continue with their usual pharmacological treatment.

The effects will be measured after a treatment of 20 sessions (twice a week). Results will be obtained by analyzing EEG parameters (EEG amplitude and frequency) and cognitive functions (BACS and MoCA). On the other hand, at the end of the 20-session program, tests will also be administered to assess the symptomatology of the severe mental disorder suffered by the person (PANSS) to assess the effects of the program on these variables.

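### Government referral is given as the reason assignment is random, no sequence generation or concealment is described, and the numbers left after losses (26 and 21) are presented as the numbers assigned

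*Combined protocol and SAP*

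**What the plan says.** **How patients reach an arm.** Population characteristics (Study methodology, 2.a) gives the only stated basis for random assignment: "The assignment will be made randomly, as they will be referred by the Government of the Canary Islands". It supports this with a reference to a section of the regional mental health plan on coordination between services. The same section introduces the referral route with the words "Patients who will participate in the dance therapy program will be referred to the Canarian Association of Creative Therapies (ASCATEC", and describes no separate route for controls.

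**Statements that the trial is randomised.** Design refers to patients "who will be randomly assigned into two groups, 1 intervention group receiving dance therapy (n=26", with 21 in the control group and a total of at least 47. Workplan says "The people with SMD will be randomly assigned to an experimental group" or to control. Data Collection also refers to randomisation when it times the baseline tests. None of these sections says how the sequence is produced, who holds it, or how it is kept from those who recruit.

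**Ratio and numbers.** Sample size calculation (2.e) describes "the ratio being a value of 1, as these are two groups with equal sample sizes", and arrives at 28 per group. It then applies expected losses of 10% and 25%. The experimental group "would be left with a final (n) of 26 participants", and the control group, "after expected loss to follow-up of 25% out of 28 equals 7, would be left with a final (n) of 21 participants". Workplan takes these as the groups that start: "The 26 people with SMD in the experimental group will participate in a 10-week intervention program". It also has the baseline tests done on 47 patients.

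**The concern.** The sentence in 2.a makes referral the reason for randomness. Referral through mental health units is an administrative and clinical decision. If it settled the arm, the people who refer would be choosing who gets dance therapy, and patients likely to do well could be steered towards it. Without concealment, the same risk arises at enrolment even where a proper list exists.

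The comparison depends heavily on this. H1a and H1b are claims of dance therapy against control. The rank tests in the statistical analysis section make no covariate adjustment, and the mixed models that follow are given no named covariates. Flawed allocation cannot be put right once patients are enrolled.

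The numbers raise a second problem. Anyone drawing up the list finds a 1:1 ratio with 28 + 28 in one section, and 26 and 21 described as the numbers assigned in two others. Allocating 26 and 21 would mean that the expected losses come off twice.

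**Working it through.** **Mechanism.** Setting the sections side by side:

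- Population characteristics: random because referred. This is a reason, but not a valid one.
- Design and Workplan: randomly assigned, no method.
- Data Collection: mentions randomisation, no method.
- Inclusion and exclusion criteria: one list for everybody, and unwillingness to attend dance therapy excludes. This suggests a single pool divided afterwards, but does not say how.

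The intention is clear. A valid mechanism and any concealment are absent.

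**Numbers.** Inputs, all from Sample size calculation: one-sided alpha 0.05, power 80%, ratio 1, SDs 2.822 (intervention) and 2.588 (control), minimum response 2, losses 10% and 25%.

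1. The SDs reproduce. The sample SD of 23.4, 18.9 and 18.2 is 2.822; that of 14.98 and 11.32 is 2.588.

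2. Patients per group: n = 2 × [SD × (1.645 + 0.842) / difference]², with difference 2.
   - SD 2.822: n = 24.6, rounded up to 25. Raised for 10% loss: 25 / 0.90 = 27.8, so 28.
   - SD 2.588: n = 20.7, rounded up to 21. Raised for 25% loss: 21 / 0.75 = 28.

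   This gives the plan's 28 in both arms. Other readings tried do not fit: taking the difference equal to the SD gives 13 per group; a two-sided test with difference 2 gives 36 and 36 after losses; both SDs in one one-sided formula give 22.7 per group. So 28 + 28 = 56 appears to include the losses already, and is the number to allocate.

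3. The plan then deducts the losses: 28 × 0.90 = 25.2 (written as 26) and 28 × 0.75 = 21. Hence 26 + 21 = 47, a ratio of 26/21 = 1.24 to 1. These are expected numbers remaining.

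4. If 26 and 21 were instead the numbers allocated, the plan's loss rates leave 26 × 0.90 = 23.4 and 21 × 0.75 = 15.75, about 39 in all.

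5. One-sided power = Φ{2 / [SD × √(1/n₁ + 1/n₂)] − 1.645}:

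| Numbers analysed | SD 2.822 | SD 2.588 |
|---|---|---|
| 26 and 21 | 78% | 84% |
| 23.4 and 15.75 | 70% | 77% |

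For the last row, √(1/23.4 + 1/15.75) = 0.326. The first term is then 2 / (2.822 × 0.326) = 2.17 or 2 / (2.588 × 0.326) = 2.37. Subtracting 1.645 leaves 0.53 or 0.73.

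**The case against.** The best defence is that 2.a is about the population, and that its word for assignment may be a loose rendering of referral or selection. Three other sections speak of randomisation, and the cited regional plan may say more. That much stands. A reader might infer that the trial will not be randomised; the documents do not support this. But if the sentence is only about referral, the one stated basis for random assignment disappears and nothing takes its place. A plan outside the documents cannot be assumed to supply it.

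A reader might also infer that there is no usable ratio, so that no list could be drawn up. That is wrong: Sample size calculation states a ratio of 1, and a 1:1 list can be made from it. The fault is that Design and Workplan carry forward different numbers. Design calls 47 a minimum, so allocating 56 would not breach it. Even so, Design attaches 26 and 21 to the act of assignment, and Workplan tests 47 at baseline.

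A third tempting reading is that 28 is the number needed for analysis and should have been raised to 32 and 38 (28 / 0.90 and 28 / 0.75, rounded up). The plan's wording invites this, but 28 in both arms reproduces only if the losses are already included.

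It is fair to say that the 23 and 16 scenario follows only if Design and Workplan are taken at their word over the derivation in 2.e. It says nothing about the size of any selection bias.

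Finally, Data Collection describes the intervention group as having psychosis without comorbidities, while 2.a admits any type of diagnosis within severe mental disorder. A reader might infer that the arms are selected differently. The single eligibility list argues against that, and excluding serious comorbid mental disorder partly explains the phrase. It is a wording inconsistency.

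**Conclusion.** The point holds and should be corrected before enrolment. The stated justification for random assignment is invalid, and no sequence generation or concealment is described. The resulting risk is selection bias in the comparisons for H1a and H1b. Its size cannot be estimated from the documents, and its occurrence depends on whether 2.a is followed literally.

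Separately, the plan's 1:1 ratio with 28 + 28 conflicts with the 26 and 21 given as assigned. If 26 and 21 are the numbers remaining, one-sided power is about 78% to 84%, close to the 80% intended. If they are the numbers allocated, it is about 70% to 77%.

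These powers rest on the plan's own inputs: a one-sided test, a difference of 2, the stated loss rates, and SDs that were computed from group means of PANSS negative symptoms in other studies. Whether those SDs suit this trial's cognitive outcomes is a separate question and is not judged here.

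**What to change.** - **Population characteristics:** replace the justification. Say that referral only supplies candidates, and that all eligible, consented patients are then allocated from a computer-generated, concealed list kept by an existing team member who takes no part in recruitment or testing.
- **Design, Sample size calculation and Workplan:** use the 1:1 ratio throughout. Give numbers allocated (28 + 28 on the plan's own calculation) separately from numbers expected to remain (about 25 to 26, and 21). If only 47 are to be allocated, restate the power for the numbers that would then remain.
- **Wording only:** reconcile the description of the intervention group's diagnosis in Data Collection with Population characteristics, so that one definition covers both arms.

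The allocation fix costs some protocol text and one list; it adds no patients, visits or tests. Allocating 56 means 9 more patients than the stated minimum of 47 (56 − 47).

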#### **b. Inclusion criteria**

---

 [https://www3.gobiernodecanarias.org/sanidad/scs/content/d7a0d910-4973-11e9-910bf705e6f363c5/PSMC\\_completo.pdf](https://www3.gobiernodecanarias.org/sanidad/scs/content/d7a0d910-4973-11e9-910bf705e6f363c5/PSMC_completo.pdf)

The inclusion criteria are the following:

- People diagnosed with a SMD according to the DSM-V.
- Have the capacity to decide and consent.
- Be in the age range between 18 and 65 years old.
- Do not present active consumption of toxic substances (except nicotine).
- Commitment to attendance during the entire study period from December 2023 to December 2024.

